4.2.2 Inclusion criteria: dose expansion cohort

Patients must meet ALL of the above criteria and additionally meet the following criteria:

1. Histologically proven locally advanced (unresectable) or metastatic melanoma.
2. Documented presence of either BRAF or RAS mutations, as established by validated mutation testing from tumour biopsy.
3. Evidence of measurable disease (according to RECIST v1.1, Appendix 5).

4.3 Exclusion criteria:

Patients who meet ANY of the following criteria will not be eligible to participate.

Patients who have had any of the following within the last 4 weeks:

1. Radiotherapy (except for palliative reasons), endocrine therapy (except luteinizing hormone releasing hormone (LHRH) agonists for prostate cancer), immunotherapy or chemotherapy (6 weeks for nitrosoureas, Mitomycin-C and 4 weeks for other investigational medicinal products (IMP)) before treatment. (For patients recruited to Part B (dose expansion) from Part A (dose escalation), prior treatment with CCT3833 during Part A (dose escalation) is permissible.)
2. Major surgery within the last four weeks.
3. Has been a participant in another interventional research study (involving an IMP) within the last 4 weeks, or plans to participate in one whilst taking part in this study. Participation in an observational study would be acceptable.

Patients who have any of the following:

4. High medical risk because of non-malignant systemic disease including active, uncontrolled infection.
5. Known allergy to any pharmaceutical excipients.
6. Known to be serologically positive for Hepatitis B, Hepatitis C or Human Immunodeficiency Virus (HIV). Testing for these viruses is not mandatory.
7. Impaired cardiac function or clinically significant cardiac diseases, including any of the following:

- a. History or presence of ventricular tachyarrhythmia.
 - b. Presence of unstable atrial fibrillation (ventricular response > 100 bpm); patients with stable atrial fibrillation are eligible, provided they do not meet any of the other cardiac exclusion criteria.
 - c. Repeated presence of a prolonged QTc interval > 450 ms at baseline (as calculated by Fridericia method).
 - d. Unstable angina pectoris or acute myocardial infarction in the last 12 months prior to starting study drug.

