 - e. Other clinically significant heart disease (e.g., symptomatic congestive heart failure (LVEF < 50%); uncontrolled arrhythmia; history of labile hypertension or poor compliance with an antihypertensive regimen).
8. Uncontrolled hypertension that remains uncontrolled on > 1 antihypertensive agent.
 9. Symptomatic brain metastases (if present they must have been stable for > 3 months). Such patients must not be requiring systemic corticosteroid or enzyme-inducing anticonvulsant therapy.
 10. Inability to take oral medication; impairment of GI function or GI disease that could interfere with drug absorption.
 11. Have taken potent inducers/inhibitors of CYP3A4 and CYP2C8 liver enzymes within 2 weeks of the first administration of study drug, or have conditions that require the concomitant usage of such drugs during the course of the study.
 12. Are taking warfarin as an oral anticoagulant; patients anticoagulated with low molecular weight heparin are not excluded from the trial.
 13. Female patients who are pregnant or lactating, or have the ability to become pregnant. However, those female patients who have a negative serum or urine pregnancy test before enrolment and are using highly-effective contraception during the study and for 6 months afterwards, are considered eligible. Highly-effective contraception methods include:
 - a. Total abstinence.
 - b. Male or female sterilization.
 - c. A combination of any two of the following:
 - i. Oral, injected or implanted hormonal contraception.
 - ii. Placement of an intrauterine device (IUD) or intrauterine system (IUS).
 - iii. Barrier methods of contraception: condom or diaphragm with spermicidal foam/gel/film/cream/vaginal suppository.
 14. Male patients with partners of child-bearing potential, unless they agree to take measures not to father children by using one form of highly effective contraception as defined above, during the study and for 6 months afterwards. Men with pregnant

or lactating partners should be advised to use barrier method contraception to prevent exposure to the foetus or neonate.

15. Any other condition which in the Investigator's opinion would not make the patient a good candidate for the clinical study.

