6.8.1 Intra-patient dose escalation

Patients without disease progression or significant toxicity will be eligible for intra-patient dose escalation, which may occur at the end of every second treatment cycle, after at least 56 days on treatment. Such escalation would occur in addition to the three newly recruited patients allocated to the new dose level cohort, as long as at least 28 days of safety data was available for that dose level and the dose level had not been closed due to toxicity.

The decision of intra-patient dose escalation for each patient will be fully discussed and decided by the SRC. Those patients who have a dose escalation can be counted by the SRC for the purpose of considering further escalations. Additional PK samples will be collected from patients that have dose escalation at C2 D1 of the escalated dose regimen.

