6.9 Dose modifications

6.9.1 Dose reductions

The dose of CCT3833 will be reduced to the previous dose level for any patient who experiences a DLT (which can occur during any cycle of treatment). Once the dose has been reduced, it should not be re-escalated. If any patient requires more than two dose reductions, the patient should be withdrawn from the study by the Principal Investigator.

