6.9.3 Dose expansion cohort

Once a MTD is defined in Part A, Part B, the melanoma-specific expansion phase will begin at the defined RP2D in order to define the safety, tolerability, pharmacokinetics and pharmacodynamics and provide preliminary efficacy information on CCT3833.

Patients with metastatic or locally advanced (unresectable) melanoma will be recruited into clinically and molecularly defined groups (approximately 9 in each), namely:

1. BRAF mutant, BRAF inhibitor 'treatment naïve'.

2. BRAF mutant, with progression on licensed BRAF inhibitor.
3. RAS mutant.

The total number of patients in this stage of the study will therefore be 27. Recruitment to cohorts will take place simultaneously rather than sequentially. This stage of the study will again operate at two sites, namely the Royal Marsden Hospital, London, and The Christie Hospital, Manchester.

Melanoma patients treated at the RP2D in the dose escalation phase of the study may continue on study treatment if re-screening confirms their eligibility. They can therefore be included in the efficacy analysis in the expansion stage of the study, in addition to, the 9 patients in the relevant cohort.

Melanoma patients treated at a dose escalation dose other than the recommended Phase 2 dose, who remain on treatment at the time of commencement of Part B, may also be re-screened and, if eligible, resume treatment at the RP2D as part of the expansion stage. Again, these patients will be recruited in addition to, the 9 patients in the relevant cohort.

Any melanoma patient identified with PD on CCT3833, who has not previously received licensed BRAF inhibitor therapy (i.e. Cohort 1), will be immediately offered treatment with the most appropriate approved alternative targeted therapy. This 'rescue route' will ensure that a patient's treatment is not compromised through trial participation.

During the expansion phase, the SRC will continue to monitor safety and will agree any action needed to refine the dose or dosing schedule.

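### Sections 6.9.1 and 6.9.3 do not agree on whether a Part A melanoma patient whose dose was reduced after a DLT may be raised to the RP2D on entering Part B

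*Combined protocol and SAP*

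**What the plan says.** **Reduction rule (6.9.1).** "The dose of CCT3833 will be reduced to the previous dose level for any patient who experiences a DLT", and this applies in any treatment cycle. The section continues: "Once the dose has been reduced, it should not be re-escalated". It states no exception for entry to Part B.

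**Roll-over (6.9.3).** Two paragraphs cover Part A melanoma patients.
- The first concerns those treated at the RP2D during escalation. If re-screening confirms eligibility they may stay on study treatment and be included in the expansion-stage efficacy analysis. It states no dose.
- The second concerns everyone else with melanoma, that is, those given some other dose in Part A, whatever the reason for it. Its permission reaches those of them "who remain on treatment at the time of commencement of Part B, may also be re-screened and, if eligible, resume treatment at the RP2D". On numbers it adds: "Again, these patients will be recruited in addition to, the 9 patients in the relevant cohort".

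**Within-patient escalation (6.8.1).** "Patients without disease progression or significant toxicity will be eligible for intra-patient dose escalation", and the SRC decides for each patient. Section 6.9.3 does not mention this rule.

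**Eligibility (4.2, 4.3).** Exclusion 1 says that "prior treatment with CCT3833 during Part A (dose escalation) is permissible" for patients moving from Part A to Part B. No criterion concerns an earlier DLT or dose reduction on CCT3833. Exclusion 15 is general: "Any other condition which in the Investigator's opinion would not make the patient a good candidate for the clinical study".

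**Analysis (5.5, 10.3.1, 10.3.5).** Every eligible patient given at least one dose is evaluable for safety. Part A toxicity is tabulated by dose level, Part B toxicity is reported for the patients recruited there, and tolerability is evaluated separately for each melanoma cohort. Nothing says how a patient who appears in both parts is shown.

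**The concern.** One section forbids raising a dose that was lowered for a DLT. Another permits a move to the RP2D for a group whose wording includes such patients. A site that reads only 6.9.3 could re-screen a patient whose DLT has resolved, find every specific criterion met, and raise the dose. A site that reads 6.9.1 first would not.

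Two things are at stake. The first is patient safety in a first-in-human trial: a known intolerant patient could be given a higher dose without a stated SRC decision. The second is the reading of Part B. Such a patient would enter a cohort of about 9 with intolerance already established in Part A, and the tolerability summary would not identify that patient.

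**Working it through.** No formal sample-size calculation underlies the trial (10.2), so this is mainly a comparison of text.

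**The plan's own counts.** 3 cohorts × 9 = 27 for Part B, and 42 + 27 = 69 for the trial. Both reproduce. Roll-over patients come on top of the 27 (10.2).

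**Which DLT patients the wording reaches.** Take a Part A melanoma patient reduced by one level after a DLT and still on treatment when Part B opens.

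1. *DLT at a level below the eventual RP2D.* The reduced dose is lower still, and the patient was never at the RP2D. The second paragraph applies directly and would permit a move above the DLT dose. This can arise because a level is non-tolerated only with 2 or more DLTs (6.5), and because DLTs in later cycles also trigger a reduction (6.9.1).
2. *DLT at the level that becomes the RP2D.* The patient has been treated both at the RP2D and at a lower dose, so either paragraph could apply. The first states no dose. The second would permit a return to the DLT dose.
3. *DLT one level above, with the RP2D set at an intermediate dose.* The reduced dose is below the RP2D. The second paragraph would permit a rise, which 6.9.1 bars, but not back to the DLT dose.
4. *DLT above the RP2D, with the reduction landing on the RP2D.* Nothing is re-escalated and there is no conflict.

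The text therefore conflicts in cases 1 and 3, is ambiguous in case 2, and is consistent in case 4.

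**What re-screening would catch.** The inclusion and exclusion criteria contain nothing on a prior DLT or reduction, and exclusion 1 permits prior CCT3833. Only exclusion 15 remains, and it is discretionary.

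**How often the precondition of case 2 could arise.** Table 5 allows at most one DLT in up to six patients at the MTD, and 6.5 requires at least 6 evaluable patients. The documents give no true DLT rate, so p is assumed between 0.05 and 0.30. With six patients:

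P(exactly 1) = 6p(1−p)^5

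P(at most 1) = (1−p)^6 + 6p(1−p)^5 = (1−p)^5(1+5p)

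P(exactly 1, given at most 1) = 6p/(1+5p)

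| Assumed p | 6p/(1+5p) |
|---|---|
| 0.05 | 0.30/1.25 = 24% |
| 0.10 | 0.60/1.50 = 40% |
| 0.15 | 0.90/1.75 = 51% |
| 0.20 | 1.20/2.00 = 60% |
| 0.25 | 1.50/2.25 = 67% |
| 0.30 | 1.80/2.50 = 72% |

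These are chances that some patient, of any tumour type, had a DLT at the declared MTD. They are not chances of the conflict. The patient must also have measurable BRAF- or RAS-mutant melanoma, still be on treatment, and pass re-screening. The documents give no figure for any of these steps. For case 1 they give no basis for a probability at all.

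**Weight in Part B if it happens.** One patient added to 9 is 1/(9+1) = 10% of that cohort, or 1/(27+1) = 3.6% of Part B.

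**The case against.** The strongest reply is that both rules can be obeyed together. Section 6.9.3 is permissive: patients may be re-screened. Section 6.9.1 is a specific limit under the same heading 6.9, and nothing in 6.9.3 sets it aside. Section 6.8.1 gives the SRC the decision on each within-patient escalation and does not exempt roll-over patients. The SRC also keeps monitoring safety during expansion, and exclusion 15 lets the investigator refuse entry. On this view all that is missing is a cross-reference.

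Much of this stands. A careful reader could reach a single answer, and the affected patient is rare. But that answer rests on inference: 6.9.3 names no exception and cites neither section, and the SRC role it does mention concerns refining the dose or schedule, not the entry of an individual.

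Two stronger readings are tempting.

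- A reader might infer that 6.9.3 sends the patient with a DLT at the RP2D back to that very dose. The documents do not support this. That patient may fall under the first roll-over paragraph, which orders no dose change, and the second only permits one.
- A reader might infer that such patients should be dropped from the Part B tolerability percentages. That sits badly with 5.5, under which every eligible dosed patient is evaluable for safety, and removing known intolerant patients could flatter tolerability.

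**Conclusion.** The inconsistency is real, but limited. The bar in 6.9.1 has no stated exception, and the permission in the second roll-over paragraph of 6.9.3 has none either. They meet most clearly for a patient whose DLT was below the eventual RP2D. For a DLT at the level that becomes the RP2D the plan is ambiguous, not plainly contradictory.

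The case is likely rare. Its probability cannot be computed from the documents, and the 24% to 72% range above describes only one precondition under assumed DLT rates. The 10% share of a cohort is conditional on the event, and on the patient being counted in that cohort's tolerability summary. For a patient entering under the first paragraph, 6.9.3 mentions only the efficacy analysis, so that share is not established there.

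This is a should-fix point: a safety instruction should not depend on which section a site reads first. It does not show that the trial's main conclusions would be wrong.

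**What to change.** **Treatment sections.** Reconcile 6.9.1, 6.8.1 and both roll-over paragraphs of 6.9.3 so that they give one answer for a Part A patient whose dose was reduced for toxicity. The text should say which paragraph covers a patient who was treated at the RP2D and then reduced, and at what dose the first paragraph intends such a patient to continue. Which clinical rule applies is for the sponsor and the SRC.

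**Analysis sections.** In 10.3.1 and 10.3.5, keep roll-over patients in the safety reporting. Show Part B tolerability both with and without them, and flag any patient with a Part A DLT or dose reduction.

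**Cost.** A few sentences in section 6 and one or two in section 10, with one additional presentation of the Part B tolerability tables. No extra patients or procedures are needed.

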6.10 Oncogene mutation sequencing

Identification of mutation status will be performed locally, from archival paraffin-embedded tumour samples. If archival tissue is not available, or is inadequate for testing, a fresh biopsy must be taken.

Historical tissue and tumour biopsies taken during the study will be sequenced for other clinically relevant mutations, either during this study, or after the reporting of this study. Patients in both the escalation and expansion stages will be asked to consent to this, and to the future potential testing of historical and biopsy tumour tissue, at the time of recruitment to the study.

6.11 Duration of treatment

Patients in Part A (dose escalation stage) may continue to receive CCT3833 as long as they are continuing to show clinical benefit, as defined by clinical or radiological (RECIST v1.1, Appendix 5) criteria.

Patients in Part B (dose expansion stage) will receive a maximum of 12 cycles of treatment. If they are continuing to show clinical benefit at this stage, treatment may be continued on a compassionate basis.

6.12 Discontinuation/withdrawal of participants from trial treatment

Each participant has the right to withdraw from the trial at any time. In addition, the Investigator may discontinue a participant from the trial at any time if the Investigator considers it necessary for any reason including:

- Pregnancy.
- Ineligibility (either arising during the trial or retrospectively, having been overlooked at Screening).
- Serious deviation of the study protocol (including persistent patient attendance failure and persistent non-compliance).
- An AE (or SAE), which requires discontinuation of the trial medication or results in inability to comply with trial procedures.
- Withdrawal of consent.
- Evidence of disease progression.
- Withdrawal by the Investigator.
- Sponsor's decision to terminate the study.

All results of the evaluations and observations to the point of withdrawal, together with a description of the reasons for withdrawal from the study, must be recorded in the medical records and in the eCRF. Patients who are removed from the study due to AEs (clinical or laboratory) will be treated and followed according to accepted medical practice. All pertinent information concerning the outcome of such treatment must be recorded in the eCRF and on the SAE report form where necessary.

6.13 Replacement of patients

Patients that withdraw but are evaluable for dose escalation decisions will not be replaced. Any patient that is withdrawn and is not evaluable will be replaced to ensure the minimum number of evaluable patients at each dose level in Part A. Patients may be replaced by another patient treated at the same dose level during the dose escalation phase if they fulfil at least one of the following criteria:

- Withdrawal from treatment prior to the end of Cycle 1 for reasons other than drug-related toxicity.
- Administration of less than 75% of planned doses of CCT3833 during Cycle 1 for reasons other than drug-related toxicity.

During Part B (the expansion stage) no replacement will be needed.

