5.5 Patient evaluability

All patients who meet the eligibility criteria and receive at least one administration of CCT3833 will be evaluable for safety.

Patients who receive less than 75% of the planned doses of CCT3833 during the first treatment cycle (for reasons other than toxicity) will not be evaluable for dose review decisions. Patients who are not evaluable may be replaced.

All patients who meet the eligibility criteria, receive at least 75% of the planned doses of CCT3833 in the first treatment cycle, and have a baseline assessment of disease will be evaluable for disease response according to the RECIST criteria v1.1 (Appendix 5). To be assigned a status of complete response (CR) or partial response (PR), changes in tumour measurement must be confirmed by repeat measurements performed no less than 4 weeks after the response criteria are met. To be assigned a status of stable disease (SD), follow-up measurements must have met the SD criteria at least once, and at least 6 weeks after the first dose of CCT3833 has been taken.

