6.4 Definition of dose-limiting toxicity

The dose-limiting toxicity (DLT) is defined using the National Cancer Institute's (NCI) Common Terminology Criteria for Adverse Events (CTCAE) version 4.03 (Appendix 4). DLTs identified in Cycle 1 of treatment will inform the decision to dose escalate through the increasing dose levels. Significant toxicities and DLTs in later cycles will be considered throughout the treatment period and in determining the recommended Phase 2 dose.

A DLT is defined as a probably or highly probably drug related toxicity as detailed in Table 8.

Table 8: Dose-limiting toxicity definitions and criteria

Toxicity	Criteria
Any toxicity causing a decrease in treatment dose intensity	Inability to deliver > 75% of the planned dose intensity in a cycle due to CCT3833-related toxicity
Haematology	
 • Grade 4 neutropenia for > 1 week • Grade 4 thrombocytopenia or grade 3 thrombocytopenia with bleeding • Febrile neutropenia • Grade 4 anaemia (unless a specific cause of blood loss is identified)
Cardiovascular	
 • Any grade 3 or above • Hypertension (grade 3 or above) lasting more than 2 weeks despite optimal treatment
Skin	Any grade 3 or above, persisting for > 7 days despite optimal treatment
Metabolic	Grade 3 or above hyperglycaemia (measured in the fasted state)
Any other drug related G3/4 toxicity except:	
 • Alopecia • Nausea that is sub optimally managed • Vomiting that is sub optimally managed • Diarrhoea that is sub optimally managed • Constipation that is sub optimally managed
Any other toxicity that is considered dose-limiting in the view of the Investigator	

Baseline laboratory values are those reported before the first dose of CCT3833.

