6.6 Dose escalation scheme

Patients will be enrolled to ensure a minimum of 3 and a maximum of 6 evaluable patients per cohort. The dose level of CCT3833 will be assigned using all available data by the Sponsor in conjunction with the Safety Review Committee (SRC). Dose assignment will be made after considering the number of patients already enrolled at the current dose level, the number of DLTs (and any other drug related AEs) observed at the current dose level, and the number of patients enrolled who are at risk of developing a DLT.

The first patient in all cohorts will be treated for 7 days taken from Day 1, before the second and third patients can take their first dose of CCT3833 in parallel. Patients who receive less than 75 % of their planned doses in Cycle 1, taken from Day 1 onwards, for reasons other than toxicity will not be evaluable for assessment of DLT for dose review decisions and will be replaced in the cohort.

In order to make the decision to escalate the CCT3833 dose, three evaluable patients must have completed one cycle of treatment (28 days). The time between cohorts is therefore approximately 6 weeks.

The dose increases between cohorts will be up to 100%, i.e. doubling of the dose (dosed on a flat scale and not by body weight or body surface area), until a probable or highly probable drug-related CTCAE v4.03 (Appendix 4) Grade 3 AE (or grade 4 haematological toxicity) is reported. Subsequent dose increases between cohorts will be driven by reported safety data and available PK and PD data. The available PK data for all patients will be reviewed as part of the dose escalation data. PK data for a minimum of two patients in the current cohort will be required to inform dose review decisions. PK data for a minimum of two patients from the previous cohort will also be required.

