6.8 Dose escalation decisions

An SRC meeting will be triggered when three patients have had the opportunity to complete the first cycle of treatment. The safety data including a list of DLTs and all AEs will be reviewed, along with all other available data (including PK analyses from at least two subjects), in order to make the decision. When sufficient data are available to assess the existing cohort, the next dose level will be assigned according to the following:

- Proceed with dose escalation: If the data is available from three patients who have been treated in a cohort and no DLTs have been observed at that dose level, then dose escalation can be considered.
- Expand the cohort to further explore the dose level: If the data is available from three patients who have been treated in a cohort and one DLT has been observed at that dose level, then the cohort will be expanded to include six patients.
- De-escalate the dose: If two DLTs have been observed at any dose level, the dose will be de-escalated to either the previous dose level (expanding to include up to six patients) or an intermediate dose level will be explored. If the previous dose level already included a cohort of six patients then this will be identified as the MTD.
- Explore different dosing schedules or formulations: If the daily continuous dosing treatment schedule is not tolerated, then the frequency of dosing for subsequent patients may be reduced. Dose escalation will continue at the reduced schedule.
- Stop the dose escalation phase of the study.

The decisions of the SRC on the next dose level and/or dosing schedules will be documented and provided to the Investigators prior to dosing any new patients.

The RP2D to be further evaluated in Part B (expansion phase) will be determined by the SRC based on the MTD and observed safety profile, PK and PD data. During the expansion phase, the SRC will continue to monitor safety and will agree any action needed to refine the dose or dosing schedule.

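### The rules for who counts in the DLT denominator conflict across sections 5.5, 6.6 and 6.13, and a patient under-dosed for possibly related toxicity can count as DLT-free

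*Combined protocol and SAP*

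**What the plan says.** Section 5.5 takes out of dose review decisions "Patients who receive less than 75% of the planned doses of CCT3833 during the first treatment cycle (for reasons other than toxicity"), and adds that "Patients who are not evaluable may be replaced". Section 6.6 repeats the 75% rule, counted from Day 1, but makes replacement mandatory: such patients, if under-dosed "for reasons other than toxicity will not be evaluable for assessment of DLT for dose review decisions and will be replaced in the cohort". It also sets the condition for escalating: "three evaluable patients must have completed one cycle of treatment (28 days").

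Section 6.13 opens by saying that patients who withdraw but are evaluable are not replaced, and that those who are withdrawn and not evaluable are. It then lists two criteria, either of which allows replacement: "Withdrawal from treatment prior to the end of Cycle 1 for reasons other than drug-related toxicity" and "Administration of less than 75% of planned doses of CCT3833 during Cycle 1 for reasons other than drug-related toxicity".

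On attribution, section 6.4 states: "A DLT is defined as a probably or highly probably drug related toxicity as detailed in Table 8". Table 5 repeats that attribution in its MTD definition. Section 9.1.3 defines drug-related more widely, to include events assessed as possible. The dose-intensity row of Table 8 makes failure to deliver more than 75% of planned intensity a DLT when it is due to CCT3833-related toxicity, without giving a causality level.

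Section 6.8 says that "An SRC meeting will be triggered when three patients have had the opportunity to complete the first cycle of treatment". Its escalate and expand rules count three patients who were treated and do not mention evaluability. Section 6.5 requires at least six evaluable patients for the MTD.

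**The concern.** Each escalation decision can rest on three patients, and dose increases can reach 100%. With so few patients, whether one of them counts, is ignored or is replaced can decide the step. The trial is open-label, so if the sections give different answers the choice falls to people who already know that patient's outcome.

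The more serious case is the patient who could not take the drug. If missed doses are put down to toxicity graded only possible, the wording can leave that patient in the denominator with no DLT. Inadequate exposure is then read as evidence that the dose was tolerated, and the error runs towards escalation.

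**Working it through.** No figure stated in the plan is in dispute, and the plan gives no DLT rate or operating characteristics to reproduce. The check compares the wording and then does a short binomial calculation.

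**Threshold.** A cycle is 28 days (6.1) with once-daily dosing, so 75% is 0.75 × 28 = 21 doses. Twenty doses is 20/28 = 71.4% (below the threshold), 21 is 75.0% and 27 is 96.4%. Another schedule would change the counts but not the conflict.

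**Passages side by side**, for patients with no recorded DLT:

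| Patient | 75% rule (5.5, 6.6) | 6.13, opening sentences | 6.13, criteria | 6.6, completed cycle |
|---|---|---|---|---|
| A. Withdraws after 21–27 doses, not for drug-related toxicity (e.g. progression) | Evaluable | Not replaced | Replaceable (first criterion) | Not met |
| B. At most 20 doses, toxicity judged unrelated | Evaluable if toxicity means any toxicity; not evaluable if it means drug toxicity | Follows the 75% rule | Replaceable (second criterion) | Can be met if evaluable |
| C. At most 20 doses, toxicity graded possible | Evaluable | Not replaced | Not replaceable, since possible counts as drug-related | Can be met |
| D. At most 20 doses, no toxicity involved | Not evaluable | Replaced if withdrawn | Replaceable | Not met |

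Patient A gets incompatible answers, two of them inside 6.13. Patient B depends on an undefined word. Patient C is treated alike by 5.5, 6.6 and 6.13, but the shared result is that an under-exposed patient counts as DLT-free: the 6.4 attribution is not met, and Table 8's dose-intensity row does not say whether possible is enough. Patient D is handled consistently, except that replacement is optional in 5.5 and mandatory in 6.6.

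**Size, as a conditional illustration.** Let p be the true DLT rate (an assumption) and let patients be independent. With three informative patients, P(0 DLTs in 3) = (1 − p)³. If one of the three gives no information but is counted as clean, it is (1 − p)². The difference is p(1 − p)².

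Reading 6.5 and 6.8 so that a level clears with 0/3, or with 1/3 followed by 0/3:

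- all informative: (1 − p)³ + 3p(1 − p)² × (1 − p)³
- one uninformative in the first three: (1 − p)² + 2p(1 − p) × (1 − p)³

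| p | P(0/3), all informative | P(0/3), one not | Level clears, all informative | Level clears, one not |
|---|---|---|---|---|
| 0.20 | 0.512 | 0.640 | 0.709 | 0.804 |
| 0.30 | 0.343 | 0.490 | 0.494 | 0.634 |
| 0.33 | 0.301 | 0.449 | 0.434 | 0.582 |
| 0.40 | 0.216 | 0.360 | 0.309 | 0.464 |
| 0.50 | 0.125 | 0.250 | 0.172 | 0.312 |

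Over p from 0.20 to 0.50 the rise in P(0/3) is smallest at 0.50 (0.125) and largest at p = 1/3, where p(1 − p)² = 4/27 = 0.148.

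**The case against.** A reader might infer that 6.8 is a further, looser definition under which three merely treated patients suffice to escalate. The documents do not support that. Section 6.8 defines nothing: it says when the committee meets and what it may consider. Section 6.6 states the binding condition of three evaluable patients with a completed cycle, and 6.7.2 also speaks of a completed 28-day window. The looser wording in 6.8 should be aligned, but it is not a separate conflict.

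The word toxicity in 5.5 and 6.6 need not mean toxicity of any cause. In a single-agent trial it may mean drug toxicity, and on that reading 5.5 and 6.6 come close to 6.13. This reduces patient B to an ambiguity. It does not help patients A or C.

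Table 8's dose-intensity row, and its investigator-judgement row, are aimed at the patient who cannot take the drug, and the committee reviews all adverse events, not only DLTs. Both are real protections. But both rows stand under the 6.4 statement requiring probable or highly probable attribution, and committee review catches such a case by judgement rather than by rule.

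The calculation assumes one wholly uninformative patient among the first three. Patient A is not that: 21 to 27 doses without a DLT is substantial information. The documents do not say how often patients such as A, B or C would arise.

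**Conclusion.** The point holds. The rules contradict each other for the early withdrawal after 21 to 27 doses, are ambiguous for under-dosing from toxicity judged unrelated, and leave a gap for under-dosing from toxicity graded possible. The first and third stand on the text without any help from 6.8. Because these rules set the denominator for escalation, they should be corrected before cohort decisions rely on them.

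The rise of 12.5 to 14.8 percentage points in P(0/3), over assumed true DLT rates of 20% to 50%, applies only if one of the first three patients contributes nothing and is counted as clean. It is an upper-end figure, closest to a heavily under-dosed patient C. A reader might take it as the bias in the MTD, the primary endpoint. It is not: it describes the escalation step, and 6.5 requires six evaluable patients before an MTD is declared.

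**What to change.** Write one definition of a DLT-evaluable patient and refer to it in 5.5, 6.5, 6.6, 6.8, 6.13 and the DLT table of 10.3.1, which at present names no denominator. It should ensure that a patient without a DLT counts as having tolerated the dose only if both the stated minimum exposure and the Cycle 1 observation period are met. Use one verb for replacement throughout, remove the clash between 6.13's opening sentence and its first criterion, and have 6.8 count evaluable patients as 6.6 does.

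State explicitly how under-dosing for toxicity that is not a DLT is classified, including toxicity graded possible, and align this with Table 8's dose-intensity row. The choice of attribution rule is the sponsor's. Simply deleting the toxicity exceptions would not be enough: patients with toxicity short of a DLT would be replaced and drop out of the denominator, which can itself favour escalation. Their events should therefore go to the safety review committee even when the patient is replaced.

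The change is to protocol wording. Its cost is an occasional replacement patient and a short delay to a cohort.
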